11.2.2 Primary Outcome Analysis

Safety outcomes: quality of images received, assessed by clinicians at 30 days(a quality image is one that can be used to make a clinical decision). These will be reported using frequencies and percentages.

Acceptability outcomes: clinician and patient satisfaction using surveys and interviews at day 30. The interviews will investigate the acceptability of the intervention including attitude, burden, perceived effectiveness, ethicality, intervention coherence, opportunity costs and self-efficacy and will be analysed using qualitative methods. Will also collect acceptability of being involved as a study participant. Survey variables that are continuous will be reported with means & 95% confidence intervals (95% CI), if shown to be normally distributed, using a normality plot, otherwise will be reported with medians & Interquartile Ranges (IQR). The categorical variables will be reported with frequencies & percentages.

Feasibility outcomes: recruitment rate, adherence with the module (intervention group only), loss to follow-up. Adherence will be reported as the number and percentage of adherent patients in the intervention group. To be adherent a patient needs to submit one photo with a completed questionnaire within the 30 day period. This will be compared with the progression criteria defined below. The definitive study will proceed (or not) based on these outcomes. The number and

percentage of eligible patients recruited to the study will be reported. All feasibility outcomes will be reported with 95% confidence intervals.

Progression criteria

Criteria:	Do not proceed	Proceed with changes	Proceed		
Recruitment	<10% of eligible patients	between 10% and <25% of	at least 25% of eligible		
	consent	eligible patients consent	patients consent		
Adherence with	<40% of intervention	between 40% and <80% of	at least 80% of		
the module	patients submit one or	intervention patients	intervention patients		
	more images	submit one or more images	submit one or more		
			images		
Loss to follow-up	<10% of intervention	between 10% and <60% of	at least 60% of		
	patients complete the	intervention patients	intervention patients		
	study	complete the study	complete the study		

Economic modelling outcomes: Will include number and severity of wound problems/infections, wound-related hospital readmission, prescribed antibiotics, time to review images, further surgery to treat wounds, prescribed wound treatments, clinic visits, GP visits, patient travel time and quality of life.

11.2.3 Secondary Outcome Analysis

Safety outcomes. More detailed discussion about reasons for compliance/non-compliance will be explored in the staff surveys and interviews and the patient intervention group surveys and interviews (these will not form part of the statistical analysis). Survey data will be analysed using descriptive statistics, and qualitative data from the interviews (which will not form part of the statistical analysis) will analysed using thematic analysis.

Feasibility outcomes: access/barriers to participation and willingness of participants to be randomised, and attrition rates and time and resources required to conduct telephone assessments to patients and phone calls to GPs to collect antibiotic data. To contribute to sample sizes for a definitive trial - numberof wound problems/infections will be collected. Wound severity, wound-related hospital readmission, further surgery to treat wounds, prescribed wound treatments, prescribed antibiotics, clinic visits, GP visits will also be collected for the economic analysis (?).

Other secondary outcomes: number of photos received (per patient), number of requests (for images) complied with - intervention group only, number photos initiated by patients (intervention group only), number of follow-up requests.

For all secondary outcomes, continuous variables will be reported using descriptive methods such as means & 95% confidence intervals (95% CI). Categorical variables will be reported with frequencies & percentages.

11.3 Subgroup Analyses

There will be no subgroup analyses.

11.4 Adjusted analyses

There will be no adjusted analyses.

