4. TRIAL DESIGN

Two-centre, unblinded parallel-group randomised feasibility study with safety and acceptability outcomes comparing the AI module with standard care.

A total of 120 patients from will be recruited to the trial over a ten-month period. Patients will be enrolled onto the study and randomised after surgery but prior to discharge or up until day five after surgery – whichever comes first. Mixed-block 1:1 randomisation stratified by site and sex managed by Derby CTSU. Patients and staff will be aware of group allocation status.

Patients in the control group will have standard post-operative wound care follow-up. Patients in the intervention group will receive digital surgical wound monitoring with the AI module for 30 days after surgery and also standard post-operative wound care follow-up.

Standard wound follow up and the Isla digital wound monitoring platform will last for 30 days after surgery. Patients in the intervention group will be contacted via SMS text message seven days, fourteen days and twenty-one days after surgery with the link request remining open for 6 days until the next request is sent out. The exception being the last request link which will remain open until 30 days after surgery. For each request, patients are asked to submit a photo of their wound and complete the modified UKHSA wound surveillance questionnaire.⁵

At consent will collect baseline quality of life data (SF-6Dv2)

After 30 days we will collect the following data:

- online satisfaction and quality of life survey with participants in both groups
- online satisfaction survey with staff
- interviews (focusing on satisfaction and experience) with a subsection of 10 patients from both groups – 20 in total
- interviews (focusing on satisfaction and experience) with a subsection of 10 staff
- •
- Phone call to all patients to discuss their wound and any treatments or healthcare interventions / engagement they may have had. (

After 60 days we will collect the following data:

- Medical case note review for all patients to identify re-admissions or further surgery
- Patient phone call to discuss their wound and any treatments or healthcare interventions / engagement they may have had and quality of life.

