7.2 Consent

Potential participants will be identified by the usual care team through screening surgical admissions lists and given brief information about the study at admission and when they are on the postoperative ward after surgery. If they express an interest in taking part, we will provide a leaflet, discuss the study with them, and answer any questions. This will be done by an appropriately delegated member of the team. The information will make it clear that the decision for whether they are allocated the AI module, or not, will be random, and to ensure that they are happy with that, to encourage retention. For patients admitted pre-operatively, information will be provided pre-operatively giving a minimum of 24 hours between receiving information about the study and seeking consent. For patents transferred in on the day of surgery, information will be given post-operatively with a minimum of 24

hours before consent is sought. We will obtain written consent after surgery before collection of any study data and randomisation. Participants will be asked at enrolment how they wish to receive dissemination information about the study (text/email/post). Participants who complete data collection will be offered £40 for their time. We will contact patients via email or telephone to obtain their bank details in order to process reimbursement for their participation in the study. We will not recruit patients who are unable to give consent.

Participants are free to decline involvement without giving reason, although where reasons are given, these will be collected as part of screening data.

If participants do not wish to participate, they will continue to receive standard post operative care and their standard of care will not change.

Informed consent will be obtained before any trial activities commence including data collection.

The Principal Investigator (PI) retains overall responsibility for the informed consent of participants at their site and must ensure that any person delegated responsibility to participate in the informed consent process is duly authorised, trained and competent according to the REC approved CIP, principles of Good Clinical Practice (GCP) and Declaration of Helsinki and in accordance with the study Delegation of Responsibilities Log.

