7.3 The Randomisation Scheme

Participants will be assigned to the intervention or control group, using stratified 1:1 randomisation with mixed block sizes to maximise the chances of equal allocation to groups. The participants will be stratified by site and sex (Male, Female, Intersex). Emergency unblinding will not be required as the study will not be blinded. Randomisation will take place at enrolment.

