11.2.1 Summary of Demographic/Baseline Data and Flow of Patients

Descriptive statistics will be presented to summarize the distribution of demographic and baseline variables across each of the randomisation groups. With the exception of quality of life, which will be analysed as part of the economic analysis, the continuous baseline variables (age, height, weight, BMI) will be reported with means & 95% confidence intervals (95% CI), if shown to be normally distributed,

using a normality plot, otherwise will be reported with medians & Interquartile Ranges (IQR). The categorical and ordinal variables (gender, ethnicity, English speaker, location (urban/rural), socioeconomic status, disability, co-morbidities, smoking status, skin tone, residential status, surgical procedure, procedure type, Access to smartphone, assistance required to take photos?, given smartphone or ipad, comorbidities) will be reported with frequencies & percentages.

A Consolidated Standards of Reporting Trials (CONSORT) flow diagram will be produced, showing the frequency of patients/ participants;

- Assessed for eligibility,
- Frequency of each reason for not being eligible,
- Found eligible,
- Approached,
- Excluded before consent (and the frequency of each reason for exclusion),
- Consented,
- Excluded before randomisation (and the frequency of each reason for exclusion),
- Randomised,
- Allocated to each randomisation group,
- That received each allocated intervention,
- That did not receive each allocated intervention,
- Completed each follow up assessment (and the frequency of each reason for non-completion) for each analysis group,
- Analysed for each analysis group,
- Not analysed (and the frequency of each reason for not being analysed) for each analysis group.

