11.8 Other Statistical Considerations

A health economic analysis plan and early model have been prepared and have informed the design of this study particularly with respect to data collection. See next section for details of the economic evaluation.

Adverse device effects and adverse events , will be reported using frequencies and percentages.

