11.9 Health Economic Evaluation

An economic investigation was included as the provision of the intervention will involve additional upfront direct costs. The intervention is unlikely to be widely adopted unless it can be shown to be cost-effective. In order for the intervention to be cost effective, the initial upfront cost will need to be offset by savings later in the clinical pathway and/or deliver positive impacts on health outcomes. The economic investigation will comprise two stages: an initial scoping exercise and an economic evaluation on completion of the clinical study. The scoping exercise has been undertaken to inform

the design of this study. This involved a search for relevant economic evaluations and existing evidence base, the development of an early model and drafting of a health economic analysis plan. The economic evaluation will compare health outcomes and costs in the intervention and control arms using a probabilistic decision model. This will provide an estimate of the probability of cost-effectiveness of the intervention compared to standard of care and identify key parameters for cost-effectiveness for further investigation in a clinical trial. We will also explore the impact of different models of providing the intervention service.

12 MONITORING, AUDIT & INSPECTION Monitoring plan

The Investigator(s) must ensure that source documents and other documentation for this study are made available to study monitors, the REC or regulatory authority inspectors. Authorised representatives of the Sponsor and competent authority may visit the participating sites to conduct audits/ inspections.

Monitoring and source data verification will be conducted by the Derby CTSU according to the study monitoring plan. The extent and nature of monitoring will be determined by the study objectives, purpose, design, complexity, blinding, number of patients and sites, and endpoints.

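### Section 11.4 bars all adjusted analyses without exception; it should let any between-arm SF-6Dv2 comparison in the economic evaluation be adjusted for the baseline score, site and sex

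*Protocol*

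**What the plan says.** Protocol Section 11.4 consists of one sentence: "There will be no adjusted analyses". It names no outcomes and allows no exception.

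The same chapter contains the only analysis described as comparing the arms. Section 11.9 says: "The economic evaluation will compare health outcomes and costs in the intervention and control arms using a probabilistic decision model". Quality of life is listed among the economic modelling outcomes both in Section 3.0 (Primary Outcomes) and in Section 11.2.2 (Primary Outcome Analysis).

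SF-6Dv2 is measured three times on each patient:
- Baseline. Section 4: "At consent will collect baseline quality of life data (SF-6Dv2". Section 7.2 places written consent "before collection of any study data and randomisation".
- Day 30. Section 4 lists an "online satisfaction and quality of life survey with participants in both groups".
- Day 60, by phone call. The schedule in Appendix 1 marks SF-6Dv2 at baseline, 30 days and 60 days.

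On the randomisation factors, Section 7.3 says: "The participants will be stratified by site and sex (Male, Female, Intersex". Baseline quality of life is not among them.

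Two passages send quality of life elsewhere. Section 11.2.1 sets it apart from the descriptive baseline summary: "With the exception of quality of life, which will be analysed as part of the economic analysis". Section 11.8 says: "A health economic analysis plan and early model have been prepared and have informed the design of this study". That plan is not available here.

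**The concern.** For the feasibility, image and acceptability outcomes, the bar in 11.4 does no harm: they are reported descriptively and no arm effect is estimated. The economic evaluation is different. It contrasts the arms, and one of its inputs is a score that is also available at baseline. If 11.4 binds that contrast, follow-up SF-6Dv2 may not be adjusted for the same patient's starting value or for the two stratification factors.

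At stake is the precision of a quality-of-life difference that may enter the decision model. Section 11.9 says the model will yield the likelihood that the intervention is cost-effective and show which parameters matter most for a later trial. An arm difference that carries part of a chance baseline gap, with a wider interval than the data require, makes both outputs less informative.

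The Protocol does make exceptions where it wants them: 11.2.1 sets quality of life apart from the baseline summary, and 11.6 sets adverse events apart from analysis by allocation. Section 11.4 has no such clause.

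**Working it through.** **The plan's own figures.** The only stated precision figures are for proportions in Section 11.1: 60/120 with 95% CI 41% to 59%, and 30/60 with 37% to 63%. Exact binomial intervals are 40.7% to 59.3% and 36.8% to 63.2%, so both reproduce. Neither concerns SF-6Dv2. The Protocol gives no SD, correlation or target difference for it.

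**Inputs.** From the Protocol: 60 patients per arm (11.1) and visits at baseline, day 30 and day 60 (Section 4, Appendix 1). Assumed: correlation ρ between any two visits of 0.3, 0.5 or 0.7, equal SDs at the three visits, and complete data. Results are in SD units. The baseline score is treated as measured before allocation, because Section 4 ties it to consent and Section 7.2 puts consent before randomisation.

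**Step 1: chance imbalance at baseline.** The standard error of the arm difference is √(2/60) = 0.183 SD. The 95% range is ±1.96 × 0.183 = ±0.358 SD. The probability of a difference larger than 0.2 SD in either direction is 27%; for 0.25 SD it is 17%.

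**Step 2: a day-30 or day-60 contrast.**
- Unadjusted 95% half-width: 0.358 SD.
- Adjusted for baseline: variance multiplied by (1 − ρ²), half-width 0.358 × √(1 − ρ²).
- Unadjusted sample size giving the same precision: 120/(1 − ρ²).
- Expected carry-over of a baseline difference d into the unadjusted contrast: ρ × d, shown for d = 0.358 SD, the edge of the 95% range.
- Change from baseline: variance multiplied by 2(1 − ρ).

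| ρ | Variance cut by adjustment (ρ²) | Adjusted half-width (SD) | Equivalent unadjusted N | Carry-over if d = 0.358 SD | Change-score half-width (SD) |
|---|---|---|---|---|---|
| 0.3 | 9% | 0.341 | 132 | 0.11 SD | 0.423 |
| 0.5 | 25% | 0.310 | 160 | 0.18 SD | 0.358 |
| 0.7 | 49% | 0.256 | 235 | 0.25 SD | 0.277 |

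Change scores match the unadjusted contrast at ρ = 0.5, do worse below it, and are less precise than baseline adjustment in every row.

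**Step 3: only if quality-adjusted life years (QALYs) are formed as an area under the curve.** The Protocol does not say that they will be. Trapezoid weights for days 0, 30 and 60 are 15, 30 and 15 days. The variance of the area is proportional to 15² + 30² + 15² + 2ρ(15×30 + 15×15 + 30×15) = 1350 + 2250ρ. Its covariance with baseline is 15 + 45ρ. The variance cut from adjustment is (15 + 45ρ)²/(1350 + 2250ρ):
- ρ = 0.3: 28.5²/2025 = 40%
- ρ = 0.5: 37.5²/2475 = 57%
- ρ = 0.7: 46.5²/2925 = 74%

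**Step 4: sensitivity to a weak baseline.** The baseline score is taken soon after surgery, by discharge or day 5, and may predict later recovery poorly. At ρ = 0 the gain for a day-30 or day-60 contrast is nil, and for an area under the curve it is 225/1350 = 17%.

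These figures cover the baseline score only. Any further gain from site and sex is not quantified, since the Protocol gives nothing to base it on.

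**The case against.** The strongest objection concerns scope. Quality of life is sent to the economic analysis, which has its own plan. Section 11.7 calls the analyses all descriptive, which cannot describe the probabilistic model of 11.9. The general statements of Section 11 may therefore be meant only for the descriptive outcomes, and 11.4 may never have been intended to reach the economic work. This stands as far as it goes: the Protocol does not settle the scope of 11.4. But it leaves an unqualified rule in the chapter that contains 11.9 and lists quality of life under primary outcome analysis. Stating the scope removes the doubt on either reading.

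A reader might infer four stronger things, which the Protocol does not support.
- *That the economic contrast will be unadjusted.* The governing plan is not available and may adjust.
- *That an unadjusted contrast is biased.* Under randomisation it is not, in expectation. The cost is precision, and error conditional on an imbalance that happens to occur.
- *That the repeated measurement is wasted, or that QALYs are affected.* Change scores could use the pairing without covariate adjustment, though less efficiently. QALYs are not mentioned. A decision model might also take utilities by health state and involve no SF-6Dv2 arm difference at all.
- *That power is lost or false positives rise.* No test of SF-6Dv2 is planned, so such figures would describe analyses that the Protocol does not contain.

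**Conclusion.** The point holds in a limited, conditional form. As worded, 11.4 rules out the standard and more precise way to estimate an SF-6Dv2 difference between arms, in the one outcome set where the Protocol says the arms will be compared. If such a contrast is made, and with ρ between 0.3 and 0.7, adjustment for baseline would reduce its variance by 9% to 49%. The gain would be less if the early post-operative score correlates weakly with later ones, and 40% to 74% if an area-under-the-curve QALY is used. The correlations, equal SDs and complete data are assumptions, so the size is a range. This is a cheap improvement to the wording. It does not show that the planned economic evaluation is flawed.

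**What to change.** Limit 11.4 and state the exception, for example:

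*No adjusted analyses will be made of the feasibility, image and acceptability outcomes, which are descriptive. Wherever SF-6Dv2, or a measure built from it, is compared between arms for the economic evaluation, the difference and its 95% CI will be adjusted for baseline SF-6Dv2, site and sex. Unadjusted means by arm will also be shown. Details are given in the health economic analysis plan.*

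Check that the health economic analysis plan agrees, and amend whichever text differs. The structure of the decision model and the way it uses utilities should stay with that plan.

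The cost is a sentence or two in the Protocol and a matching line in the health economic analysis plan. No new data are needed, since baseline SF-6Dv2, site and sex are already collected. The small downside is that patients without a baseline score drop out of the adjusted estimate unless the health economic analysis plan says how they are handled.

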11.5 Interim analysis and criteria for the premature termination of the trial

There will be no interim analyses.

The Sponsor may suspend or prematurely terminate either the entire study, or the study at an individual site, for significant reasons that must be documented (e.g. an unacceptable risk to participants or serious repeated deviations from the clinical investigation plan/ regulations). If this occurs the Sponsor shall justify its decision in writing and will promptly inform any relevant parties (i.e. participants, investigators, participating sites, REC, regulatory bodies).

11.6 Analysis Groups

Recruitment rate (including access and barriers to recruitment and willingness to be randomised) will be assessed as a percentage of all eligible patients, regardless of treatment allocation. Patients who were consented but not randomised will not be included in the recruitment rate. Adherence to the module will be assessed based on patients allocated to the intervention. Loss to follow-up will be assessed based on all randomised patients..

All other patient-based analyses will be reported based on allocated treatment, except for adverse events and adverse device events, which will be reported based on the treatment the patients received.

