11.0 STATISTICS AND DATA ANALYSIS

11.1 Sample Size Calculation

This is a feasibility study and therefore, sample size calculations cannot be calculated as there are no current data which can be used as the basis of the calculations. The feasibility outcomes for this study are all binary outcomes, for which the widest confidence intervals will occur with a proportion of 0.5 (or 50%), therefore calculating a sample size for the confidence interval based on 50% give a "worst case" estimate.

Recruiting 60 patients for each treatment group into the trial (i.e. a total of 120 patients) will enable us to estimate the recruitment and drop-out rates with a 95% confidence interval of within +/- 10% even if the rates were 50% for these two feasibility outcomes (The 95% confidence interval for a sample size of 120 patients and 60 successes, i.e. 50% of patients recruited, or 50% of patients completing the study, is 41% to 59%). If the adherence to treatment rate was 50%, the adherence rate and 95% confidence interval could be estimated to within +/- 13% (the 95% confidence interval for 30 adherent patients out of 60, as this is only relevant for patients in the intervention group, is 37% to 63%). The sample size estimations were calculated using STATA V18 with command "cii proportions". In addition, national data shows a wound problem rate of 21% (our data shows 15%) with a cardiac wound infection rate of 8%.⁸ A sample size of 120 patients should have a wound infection. This is sufficient to inform feasibility, safety and acceptability data.

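### The loss-to-follow-up progression criterion counts intervention patients only, while sections 11.1 and 11.6 define loss to follow-up on all randomised patients, so the go/no-go result depends on which section is followed

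*Protocol*

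**What the plan says.** Three parts of the protocol bear on the denominator for loss to follow-up.

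- **Section 11.6 (Analysis Groups):** "Loss to follow-up will be assessed based on all randomised patients". The sentence before it bases adherence on patients allocated to the intervention, so the section gives the two outcomes different denominators.
- **Section 11.1 (Sample Size Calculation):** "Recruiting 60 patients for each treatment group into the trial (i.e. a total of 120 patients") is said to allow the study to "estimate the recruitment and drop-out rates with a 95% confidence interval of within +/- 10" per cent. The worked interval is 41% to 59% for 60 out of 120. A second interval, 37% to 63% for 30 out of 60, is given for adherence only, on the ground that adherence concerns the intervention group alone.
- **Section 11.2.2 (Primary Outcome Analysis, Progression criteria):** the loss-to-follow-up row has three bands. *Do not proceed* begins "<10% of intervention" patients completing, *Proceed with changes* is "between 10% and <60% of" intervention patients completing, and *Proceed* is 60% or more of intervention patients completing. The text above the table says: "The definitive study will proceed (or not) based on these outcomes".

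Section 3.0 and the outcome list in section 11.2.2 attach the intervention-only restriction to adherence and not to loss to follow-up.

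**The concern.** Loss to follow-up is one of three progression criteria and a primary feasibility outcome. Two sections define it on both arms, and the table that drives the decision counts one arm. An analysis plan cannot follow both.

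A definitive two-arm trial needs follow-up in the control arm as much as in the intervention arm. As the table stands, control-arm completion could take any value without changing the result of this criterion. Conversely, good control-arm retention cannot offset a small shortfall in the intervention arm, although it would under section 11.6.

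**Working it through.** **Inputs.** 60 patients per arm and 120 in total (section 11.1). Cut-points of 10% and 60% completion (section 11.2.2). I take completion as the complement of loss to follow-up, as the table does, and exactly 60 patients per arm.

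**1. Reproduce the stated precision.** The worst case is a proportion of 0.5, with half-width 1.96 × √(0.25/n).

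| n | Half-width (normal approximation) | Interval | Exact (Clopper-Pearson) | Protocol |
|---|---|---|---|---|
| 120 | 1.96 × √(0.25/120) = 9.0 points | 41.1% to 58.9% | 40.7% to 59.3% | 41% to 59% |
| 60 | 1.96 × √(0.25/60) = 12.7 points | 37.3% to 62.7% | 36.8% to 63.2% | 37% to 63% (adherence) |

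Both stated intervals reproduce. The ±10 points hold on 120 patients. A proportion taken on 60 patients has about ±13 points, wider by a factor of √2.

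**2. Turn the cut-points into counts.**

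- On 60 intervention patients: 10% × 60 = 6 and 60% × 60 = 36.
- On 120 randomised patients: 10% × 120 = 12 and 60% × 120 = 72.

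**3. Compare the two readings.** Let I and C be the numbers of completers in the intervention and control arms. The table's *Proceed* rule is I ≥ 36. The same cut-point on all randomised patients is I + C ≥ 72. If I = C, the two rules always agree. They can part only when completion differs between arms.

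| Intervention | Control | Table as written | All randomised |
|---|---|---|---|
| 36/60 | 24/60 | 60%, *Proceed* | 60/120 = 50%, *Proceed with changes* |
| 36/60 | 12/60 | 60%, *Proceed* | 48/120 = 40%, *Proceed with changes* |
| 35/60 | 48/60 | 58%, *Proceed with changes* | 83/120 = 69%, *Proceed* |
| 48/60 | 24/60 | 80%, *Proceed* | 72/120 = 60%, *Proceed* |

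The first three rows show that the decision can change in either direction, so aligning the denominators does not simply make the rule stricter. The fourth row shows the limit of pooling: 36 of 60 controls (60%) are lost, yet both readings return *Proceed*.

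**The case against.** **The gate may be meant to differ from the reported outcome.** A criterion can have its own denominator, and the row's wording matches the adherence row above it. But the protocol does not state such an intention, and wherever else it marks an outcome as intervention-only, that outcome is not loss to follow-up. The contradiction stands.

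**Control-arm losses are not hidden.** This is correct. The CONSORT flow in section 11.2.1 reports completion of each follow-up, with reasons, for each analysis group, and attrition is also a secondary outcome. Anyone deciding on a definitive trial would see the control-arm figures. A reader might infer that control attrition goes unmeasured; the document does not support that. Only the formal criterion leaves it out.

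**Differential loss is hypothetical.** This is also fair. The 30- and 60-day calls, the 30-day survey, the three phone attempts and the payment apply to both arms. The counts in the table above are illustrations, not forecasts.

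**The stated precision is not wrong.** A reader might infer that the ±10 points in section 11.1 are lost. They are not: that figure describes the drop-out rate estimated on 120 patients, and it remains true of that estimate. Only a proportion on 60 patients has about ±13 points. Nor does the protocol require an interval to clear a cut-point, so an interval that spans 60% is no inconsistency. At the boundary the exact interval spans 60% on either denominator: 46.5% to 72.4% for 36/60, and 50.7% to 68.8% for 72/120.

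**The cut-points.** A reader might infer that the rule lets a study with 90% loss go ahead. Exactly 90% loss (6/60) falls at the edge of *Proceed with changes*, not in *Proceed*, and the recruitment and adherence criteria also apply. The 10% and 60% values look lenient and come without a rationale, but nothing in the document shows them to be wrong, and it offers no basis for particular replacements.

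**Conclusion.** The contradiction is real and lies in the protocol itself: sections 11.1 and 11.6 use all 120 randomised patients, and the progression row in section 11.2.2 uses the 60 intervention patients. It matters because the row feeds the decision on a definitive study, and the two denominators can place the same data in different bands. At 36/60 and 24/60 completers the result is 60% or 50%; at 35/60 and 48/60 it is 58% or 69%.

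The size rests on 60 patients per arm and on unequal completion between arms. With equal completion the two readings agree, and the document gives no evidence on how unequal it will be. The point does not extend to the reporting of control-arm loss, to the precision stated for the drop-out rate, or to the values of the cut-points.

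It should be fixed, but it is not critical: the study is descriptive, and one phrase in one table row is at issue.

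**What to change.** In the loss-to-follow-up row of the section 11.2.2 table, replace the reference to intervention patients with *all randomised patients* in all three bands, to match sections 11.1 and 11.6. Add a sentence that completion in each arm will be considered alongside the pooled figure when the criterion is applied, since pooling alone does not reveal unequal loss (48/60 and 24/60 is 60% overall). The by-arm figures are already planned for the CONSORT flow, so no new data are needed.

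If an intervention-only criterion is intended, keep the row, amend section 11.6 to say that the progression criterion uses the intervention arm, and state its worst-case precision as about ±13 points (37% to 63%).

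The 10% and 60% values are for the sponsor and the Trial Steering Committee to justify.

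The cost is a wording change in one table row or one sentence, carried into the analysis plan. Timing needs care: the trial summary gives a planned end of 28 February 2025 and this version is dated 19 March 2025, so the document does not show whether outcome data have been seen. The change should be dated relative to data access. If data have been seen, report the criterion on both denominators and say which was chosen afterwards.
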